### **10.3 Appendix 3: Contraceptive Guidance and Collection of Pregnancy Information**

In nonclinical animal embryo-fetal development and fertility studies, there was no evidence of teratogenicity, no skeletal or visceral malformations, and no changes in male or female reproductive and fertility indices, or in sperm parameters. In rats, decreased fetal body weight and reduced skeletal ossification were noted at the highest dose tested of 160 mg/kg/day. Peri-postnatal development studies have not yet been conducted with vadadustat, and there are no data on the transmission of vadadustat in breast milk or the effect of vadadustat on infants.

Although the potential risk of vadadustat on the developing fetus is limited based on studies to date, the trial requires that all subjects must agree to use adequate contraception throughout the trial and for 30 days after the last dose of IMP.

All WOCBP are females whose menstruation has started and who are not documented as sterile (eg, have had a bilateral oophorectomy, or hysterectomy, or who have been postmenopausal for at least 12 months).

For males and WOCBP, who are sexually active, there must be a documented agreement that the subject and their partner will take effective measures (ie, 2 different approved methods of birth control or remains abstinent) to prevent pregnancy during the course of the trial and for 30 days after the last dose of IMP. Unless the subject is surgically sterile (ie, females who have had a bilateral oophorectomy, have had a hysterectomy, or have been postmenopausal for at least 12 consecutive months; or males who have had a vasectomy), has negative pregnancy test results at Screening (serum), or remains abstinent during the trial and for 30 days after the last dose of IMP, 2 of the following approved methods of birth control must be used:

- Total abstinence from sexual intercourse (minimum one complete menstrual cycle prior to Screening Visit, throughout the trial, and for 30 days after the last dose of IMP).
- A partner who has had a vasectomy.
- Hormonal contraceptives (oral, parenteral, or transdermal) for at least 3 months prior to IMP administration or intrauterine contraception/device, throughout the trial, and for 30 days after the last dose of IMP.
- Double-barrier method (such as male condom, female condom, diaphragm, sponge, or cervical cap together with spermicidal foam/gel/film/suppository) starting at Screening Visit 1, throughout the trial, and for 30 days after the last dose of IMP.

The contraceptive method will be documented in the eCRF. Male subjects must also agree not to donate sperm from trial screening through 30 days after the last dose of IMP.

Before enrolling males and females in this clinical trial, investigators must review the below information about trial participation as part of the ICF process. The topics should generally include:

- General information.
- Informed consent form.
- Pregnancy prevention information.
- Drug interactions with hormonal contraceptives.
- Contraceptives in current use.
- Follow-up of a reported pregnancy.

Before trial enrollment, males and WOCBP must be advised of the importance of avoiding pregnancy during trial participation and the potential risk factors for an unintentional pregnancy. Subjects must sign the ICF confirming that the above-mentioned risk factors and the consequences were discussed.

A urine or serum pregnancy test for human chorionic gonadotropin (hCG) will be performed at screening on all WOCBP. If a urine test is performed and is positive, the investigator will follow-up with a confirmatory serum test.

During the trial, all WOCBP should be instructed to contact the investigator immediately if they suspect they might be pregnant (eg, missed or late menstrual cycle). Male subjects must be instructed to contact the investigator immediately, during the trial, if their partner suspects that they might be pregnant (eg, missed or late menstrual cycle).

If a subject is suspected to be pregnant before she receives IMP, the IMP administration must be withheld until the results of serum pregnancy tests are available. If the pregnancy is confirmed, the subject must not receive the IMP and must not be enrolled in the trial. If pregnancy is suspected while the subject is taking IMP (vadadustat or ESA) or within 30 days of discontinuing the IMP, the IMP must be withheld immediately (if reasonable, taking into consideration any potential withdrawal risks) until the result of the pregnancy test is known. If pregnancy is confirmed, the IMP will be permanently discontinued in an appropriate manner and the subject will be withdrawn from the trial. Exceptions to trial discontinuation may be considered for life-threatening conditions only after consultations with the Medical Monitor. If EDC is unavailable, send paper Pregnancy Form as indicated on the title page of this protocol.

Any pregnancy must be recorded on the Pregnancy Reporting Form/Exposure in Utero Form in EDC within 24 hours of awareness of the pregnancy or the investigator will call the CRO SAE hotline within 24 hours of being made aware of the pregnancy.

Pregnancy during this time frame of the female partner of a male subject should also be reported. This will require agreement and separate written informed consent on the part of the pregnant female partner.

The paper Pregnancy Reporting Form/Exposure in Utero Form must be completed with all known information regarding the pregnancy at the time of reporting. Investigative site personnel will update the form with additional information regarding the pregnancy and the outcome of the pregnancy as it becomes available until the outcome of the pregnancy is reported.

The investigator will follow the subject (or female partner of a male subject) until completion of the pregnancy. If the outcome of the pregnancy meets the criteria for classification as an SAE (ie, spontaneous abortion, stillbirth, neonatal death within 1 month of birth, or congenital anomaly [including an aborted fetus]), the investigator will also follow the procedures for reporting an SAE within 24 hours of awareness. A pregnancy in and of itself is not considered an AE; however, unexpected complications are considered AEs.

Additional information about pregnancy outcomes follows:

- Note that “spontaneous abortion” includes miscarriage and missed abortion.
- All neonatal deaths that occur within 1 month of birth should be reported, without regard to causality, as SAEs. In addition, any infant death after 1 month that the investigator assesses as related or unrelated to the in utero exposure to the IMP should also be reported.
- In the case of a live birth, the “normality” of the newborn can be assessed at time of birth.
- The “normality” of an aborted fetus can be assessed by gross visual inspection unless there are pre-abortion laboratory findings suggestive of a congenital anomaly.

Protocol required procedures for trial discontinuation and follow-up must be performed on the subject unless contraindicated by pregnancy (eg, x-ray studies). Other appropriate pregnancy follow-up procedures should be considered if indicated. In addition, the investigator must report to the sponsor, on the Pregnancy Report Form/Exposure in Utero Form, follow-up information regarding the course of the pregnancy, including perinatal and neonatal outcome. Infants will be followed for a minimum of 6 months from the date of birth.

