Trial Period	Screening		Treatment (Conversion and Maintenance)														Safety Follow-up																				
	SV1	SV2	BL								Primary Efficacy Evaluation			Secondary Efficacy Evaluation			Follow-up																				
Visit Type				0	2	4	6	8	10	12	16	20	24	26	30	34	38	42	46	50	52/ EOT	ET	ET/EOT +4 weeks														
Week	-8 to 0			0	2	4	6	8	10	12	16	20	24	26	30	34	38	42	46	50	52/ EOT	ET	ET/EOT +4 weeks														
Visit Window (Days)				± 3							± 5			± 3	± 5			± 3	± 7																		
[e]	Serum pregnancy will be tested in women of childbearing potential at SV2. Additional serum or local urine pregnancy tests should be conducted throughout the trial in sufficient number, as determined by the investigator or required by local regulations, to establish the absence of pregnancy during the trial. If positive at SV2, the subject is not eligible to enter the trial. If a subject becomes pregnant during the trial, the subject must permanently discontinue investigational medicinal product (IMP) and should attend all subsequent trial visits and be continually monitored according to the Schedule of Activities for the duration of the trial.																																				
[f]	Subjects may be retested.																																				
[g]	For eligibility, 2 Hb values measured by the central laboratory during Screening (SV1, SV2 or retest) must be between 8.0 and 11.0 g/dL (inclusive) in the US and between 9.0 and 12.0 g/dL (inclusive) Europe.																																				
[h]	Iron indices: ferritin, iron, TIBC, and TSAT.																																				
[i]	If blood is collected on a hemodialysis day, the blood draw should be completed before dialysis occurs.																																				
[j]	Liver function tests: total bilirubin, alkaline phosphatase, ALT/SGPT, AST/SGOT, and LDH.																																				
[k]	Lipids: total cholesterol, LDL, HDL, and triglycerides.																																				
D	[REDACTED]																																				
[n]	Subjects will be provided with a supply of vadadustat at the Baseline Visit and will be resupplied at subsequent visits as needed. Please refer to the drug dispensing instructions for further details.																																				

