### **5.2.2      Exclusion Criteria**

Subjects will be excluded if they meet any of the following exclusion criteria at the time points described in the schedule of assessments ([Table 1.3-1](#)).

- 1) Women of childbearing potential (WOCBP) who do not agree to practice 2 different methods of birth control or remain abstinent during the trial and for 30 days after the last dose of investigational medicinal product (IMP). If employing birth control, 2 of the following precautions must be used: vasectomy of partner, tubal ligation, vaginal diaphragm, or intrauterine device (see [Section 10.3](#)).
- 2) Male subjects who have not had a vasectomy and do not agree to the following: use of an acceptable form of contraception during the study (see [Section 10.3](#)) and for 30 days after the last dose of the study drug; to not donate semen during the study and for at least 30 days after the last dose of vadadustat.
- 3) Women who are breast feeding and/or who have a positive pregnancy test result prior to receiving IMP.
- 4) Subjects with contraindication to required trial assessment.
- 5) Subjects who, in opinion of the investigator or medical monitor, have a medical history or medical findings inconsistent with safety or trial compliance.
- 6) Anemia due to a cause other than CKD (eg, sickle cell disease, myelodysplastic syndromes, bone marrow fibrosis, hematologic malignancy, myeloma, hemolytic anemia, thalassemia, or pure red cell aplasia).
- 7) Subjects meeting cut-off of the following equivalent mean weekly doses calculated over 8 weeks prior to Screening Visit 2:
  - a) Methoxy polyethylene glycol-epoetin beta > 50 µg/week.
  - b) Darbepoetin alfa > 100 µg/week.
  - c) Epoetin analogues > 23000 IU/week.
- 8) Active bleeding or recent blood loss within 8 weeks prior to randomization.
- 9) Red blood cell transfusion within 8 weeks prior to randomization.
- 10) Anticipated to discontinue hemodialysis during the trial.
- 11) Judged by the investigator that the subject is likely to need rescue therapy (ESA administration or RBC transfusion) immediately after enrollment in the trial.
- 12) History of chronic liver disease (eg, chronic infectious hepatitis, chronic autoimmune liver disease, cirrhosis, or fibrosis of the liver).

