### 8.7.1 Clinical Laboratory Assessments

Clinical laboratory samples will be collected at the time points described in the Schedule of Assessments ([Table 1.3-1](#)) to perform the clinical laboratory assessments described in [Section 10.2](#).

Samples for laboratory assays will be sent to a central laboratory for analysis. Detailed instructions for the collection, processing, and shipment of laboratory samples will be provided by the central laboratory. If blood is collected on a hemodialysis day, blood draws should be done prior to dialysis, if applicable. The investigator is responsible for reviewing laboratory results for clinical significance.

Blood samples will be collected for the laboratory evaluations listed in [Section 10.2](#) and will be conducted during the course of the trial. For details regarding the timing of these assessments refer to the Schedule of Assessments ([Table 1.3-1](#)).

- **Pregnancy Test:** A serum pregnancy test will be performed according to the Schedule of Assessments ([Table 1.3-1](#)) for females of childbearing potential. Additional serum or local urine (if possible) pregnancy tests may be conducted throughout the trial in sufficient number, as determined by the investigator or required by local regulations,

to establish the absence of pregnancy during the trial. These results must be available and must be negative before the subject takes the first dose of IMP.

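### Contraception rules conflict: Appendix 3 lets a negative screening pregnancy test replace two methods, which exclusion 1 does not; accepted methods and screening test type also differ

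*Protocol*

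**What the plan says.** **Exclusion 1** (Protocol Section 5.2.2, repeated in the synopsis) bars any woman of childbearing potential (WOCBP) who will not agree to two methods of birth control or abstinence until 30 days after the last dose. If birth control is used, "2 of the following precautions must be used: vasectomy of partner, tubal ligation, vaginal diaphragm, or intrauterine device". The Section 5.2.2 version refers the reader to Section 10.3. Exclusion 3 separately bars women with a positive pregnancy test before dosing.

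**Section 10.3 (Appendix 3)** first says that every subject must agree to adequate contraception. It then asks sexually active males and WOCBP for a documented agreement to two approved methods or abstinence. The next sentence sets exceptions: two methods from a list are needed unless the subject is surgically sterile, "has negative pregnancy test results at Screening (serum), or remains abstinent during the trial". The list that follows contains abstinence, partner vasectomy, hormonal contraceptives or an intrauterine device, and double-barrier methods.

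**Screening test.** Section 10.3 states: "A urine or serum pregnancy test for human chorionic gonadotropin (hCG) will be performed at screening on all WOCBP", and "If a urine test is performed and is positive, the investigator will follow-up with a confirmatory serum test". Footnote e of the Schedule of Assessments (Section 1.3) states: "Serum pregnancy will be tested in women of childbearing potential at SV2", and "If positive at SV2, the subject is not eligible to enter the trial". Section 8.7.1 adds: "A serum pregnancy test will be performed according to the Schedule of Assessments" and "These results must be available and must be negative before the subject takes the first dose of IMP".

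**The concern.** The appendix that exclusion 1 cites appears to waive the requirement that exclusion 1 imposes. A negative test at screening shows only that a woman is not pregnant at that point. It cannot stand in for contraception during treatment planned to Week 52, with a contraception duty that runs 30 days beyond the last dose. The Schedule fixes only one pregnancy test, at Screening Visit 2; later tests are left to the investigator or local rules. Section 10.3 itself reports lower fetal weight and reduced ossification in rats at the highest dose tested, and says that peri-postnatal studies have not been done.

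The differing lists raise a second problem. Two sites that read the same protocol in good faith can reach opposite eligibility decisions for the same woman. Section 5.2 allows no exceptions to the criteria, and Section 10.1.7 gives enrollment against an eligibility criterion as an example of a significant deviation.

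**Working it through.** No arithmetic applies, and the plan states no figure to reproduce. The check sets the current texts side by side.

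**1. The exemption clause.**
- Section 10.3 gives three conditions joined by an or: surgical sterility, a negative screening serum test, or abstinence. Any one of them removes the two-method requirement.
- Exclusion 1 recognizes only abstinence as an alternative to two methods. A negative test is not mentioned.
- Footnote e and Section 8.7.1 require a serum test in WOCBP, negative before the first dose. Exclusion 3 bars a positive result.
- Every WOCBP properly enrolled under those texts therefore meets the negative-test condition, and the literal exemption covers essentially all of them. The one qualification is a woman screened by urine alone under the looser wording of Section 10.3, who would not have the serum result that the clause names.
- The clause also contradicts Section 10.3 itself: both the general statement that all subjects must use contraception and the sentence immediately before it.

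**2. The accepted methods.**

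| Method | Exclusion 1 | Section 10.3 list |
|---|---|---|
| Partner vasectomy | accepted | accepted |
| Intrauterine device | accepted | accepted |
| Diaphragm | accepted | within a double-barrier method with spermicide |
| Tubal ligation | accepted | not named |
| Hormonal contraceptives | not listed | accepted |
| Condoms, sponge, cervical cap | not listed | within a double-barrier method with spermicide |

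The lists overlap but differ. Take a woman who has used an oral contraceptive for at least 3 months before dosing and a condom with spermicide from Screening Visit 1, and who will continue both until 30 days after the last dose. She satisfies Section 10.3, including its timing conditions. She fails exclusion 1, because neither method is on its closed list.

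The status of tubal ligation under Section 10.3 is unsettled. The WOCBP definition gives open-ended examples of sterility, while the exemption sentence defines surgical sterility by a closed list. Tubal ligation is named in neither.

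**3. The screening test.** Footnote e and Section 8.7.1 specify serum and mention urine only for additional tests. Section 10.3 allows either, with serum needed only to confirm a positive urine result. A site working from Section 10.3 alone could omit the serum test that the Schedule requires.

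**The case against.** The strongest reply is that this is an obvious slip without practical force. Exclusion 1 is unqualified, Section 5.2 bars exceptions, and the sentence before the clause restates the two-method duty. A site reaches Section 10.3 only through a criterion that already gives a closed list. Section 10.3 calls the potential fetal risk limited on the studies to date. Counseling, reporting of suspected pregnancy and withholding of drug apply in any case.

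Much of this stands. Exclusion 1 does bind, and the requirement has not been removed. The negative-test entry requirement already exists through exclusion 3, the Schedule and Section 8.7.1, so no new criterion is needed. The urine-or-serum wording forces no breach, since a site that follows the Schedule satisfies both texts; it is the weakest of the three parts. Enrolling the woman in the example would be an eligibility deviation, not unprotected exposure.

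Two things are left unanswered. The protocol gives no order of precedence between exclusion 1 and the appendix it cites, so the cross-reference leads sites to the conflicting instruction. And the remaining safeguards detect pregnancy or limit exposure; they neither prevent pregnancy nor settle which methods qualify.

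**Conclusion.** The concern holds in all three parts on the current text. The negative-test clause contradicts exclusion 1 and its own appendix, the method lists conflict despite the cross-reference, and the permitted screening test differs between sections. Importance is low to moderate: it bears on fetal safety and consistent eligibility decisions, limited by exclusion 1 and the other safeguards. The size cannot be quantified, because the documents give neither the number of WOCBP nor the methods they use, and none is assumed here. The statement that the clause exempts essentially every enrolled WOCBP rests on reading it literally and on the serum test being done as scheduled. Sample size, alpha, power and the analyses are not affected.

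**What to change.** - In Section 10.3, delete the negative-test condition from the exemption sentence, leaving surgical sterility and abstinence. Keep the negative serum test as a separate entry requirement by pointing to exclusion 3, footnote e and Section 8.7.1.
- In Section 10.3, specify serum for the screening test, and allow urine only for additional tests.
- Use one identical list of accepted methods in the synopsis, Section 5.2.2 and Section 10.3, and say whether tubal ligation counts as a method or as sterility. Which methods to accept is the sponsor's clinical decision.

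The cost is a protocol amendment. Harmonizing the list touches an eligibility criterion, so under Section 10.6 sites would wait for ethics approval before implementing it. The two Section 10.3 edits can go in the same amendment. The consent form changes only if it repeats this wording, which cannot be checked from the protocol and SAP. Sample size and analyses stay as they are.

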## 10.4 Appendix 4: Abbreviations

Abbreviation	Definition
β-HCG	beta human chorionic gonadotropin
AE	Adverse event
AESI	Adverse event of special interest
ALT	Alanine aminotransferase (SGPT)
ALP	Alkaline phosphatase
AST	Aspartate aminotransferase (SGOT)
AUC	Area under concentration-time curve
BCRP	Breast cancer resistance protein
BL	Baseline
BUN	Blood urea nitrogen
CBC	Complete blood count
CFR	Code of Federal Regulations
CI	Confidence interval
CIOMS	Council for International Organizations of Medical Science
CKD	Chronic kidney disease
C max	Maximum observed plasma concentration
CPK	Creatine phosphokinase
CRO	Contract research organization
CRP	C-reactive protein
CS	Clinically significant
CV	Cardiovascular
DD-CKD	Dialysis-dependent chronic kidney disease
DNA	Deoxyribonucleic acid
ECG	Electrocardiogram
eCRF	Electronic case report form
EDC	Electronic data capture
EOT	End of treatment
EPO	Erythropoietin
ESA	Erythropoiesis-stimulating agent
ET	Early termination
EU	European Union
EudraCT	European Clinical Trial Data Base
FACT-An	Functional Assessment of Cancer Therapy-Anemia
FAS	Full Analysis Set
FBR	Future biospecimen research
FDA	Food and Drug Administration
GCP	Good Clinical Practice
GMP	Good Manufacturing Practice
hCG	Human chorionic gonadotropin
HF	Heart failure
Hb	Hemoglobin
HDL	High density lipoprotein
HIF	Hypoxia-inducible factor

Abbreviation	Definition
HIF-PH	Hypoxia-inducible factor prolyl-hydroxylase
HRQOL	Health-related Quality of Life
IB	Investigator's Brochure
IC 50	50% inhibitory concentration
ICF	Informed consent form
ICH	International Council for Harmonisation
ICMJE	International Committee of Medical Journal Editors
ID	Identifier
IDMC	Independent Data Monitoring Committee
I/E	Inclusion/exclusion
IEC	Independent Ethics Committee
IMP	Investigational medicinal product
IND	Investigational new drug
INR	International normalized ratio
IRB	Institutional Review Board
IV	Intravenous
IWR	Interactive Web Response
LDH	Lactate dehydrogenase
LDL	Low density lipoprotein
MACE	Major adverse cardiovascular events
MCH	Mean corpuscular hemoglobin
MCHC	Mean corpuscular hemoglobin concentration
MCV	Mean corpuscular volume
MedDRA	Medical Dictionary for Regulatory Activities
mRNA	Messenger ribonucleic acid
MTPC	Mitsubishi Tanabe Pharma Corporation
n	Number of subjects
NDD-CKD	Non-dialysis-dependent chronic kidney disease
OPDC	Otsuka Pharmaceutical Development & Commercialization, Inc.
PD	Pharmacodynamics(s)
PGI-C	Patient Global Impression of Change
PGI-S	Patient Global Impression of Severity
PGx	Pharmacogenomic(s)
PHD	Prolyl 4-hydroxylase domain
PK	Pharmacokinetic(s)
PP	Per protocol
PT	Prothrombin time
QD	Once daily
RBC	Red blood cell
RDW	Red blood cell distribution
RNA	Ribonucleic acid
SAE	Serious adverse event
SAP	Statistical analysis plan
SEAC	Safety Event Adjudication Committee
SF-36v2	36-Item Short Form

Abbreviation	Definition
SGOT	Serum glutamic oxaloacetic transaminase (AST)
SGPT	Serum glutamic pyruvic transaminase (ALT)
SmPC	Summary of product characteristics
SOC	System organ class
SV1	Screening Visit 1
SV2	Screening Visit 2
TEAE	Treatment-emergent adverse event
TIBC	Total iron binding capacity
TIW	Three times weekly
TSAT	Transferrin saturation
ULN	Upper limit of normal
US	United States
USPI	US Package Insert
██████████	██████████
WBC	White blood cell
WOCBP	Women of childbearing potential

